11.3 Safety evaluation

Data from all subjects who receive any study drug will be included in the safety analyses. Subjects who enter the study but do not take any of the study drug(s) and have had this confirmed, will not be evaluated for safety.

The severity of the toxicities will be graded according to the NCI CTCAE v4.0 whenever possible.

11.4 Interim analyses

11.4.1 Interim analysis strategy

Accrual will continue until maximum number of patients reaches or the trial is terminated according to the monitoring rules. No interim analyses are planned.

11.4.2 Efficacy

No interim analysis of efficacy will be performed.

11.5 Safety

Safety monitoring rules are detailed in Section 10.3.

11.6 Sample size and power considerations

Given 4 predefined dose levels and potential modification to dosing schedule B after treating 6 patients at dose level 1 with schedule A, it is anticipated that up to 30 eligible patients are required for the dose-finding portion of this phase I trial.

12 Regulatory Considerations

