Dose level 1	1 mg orally on days 1-28	1 mg orally on days 1-21
Dose level 2	2 mg orally on days 1-28	2 mg orally on days 1-21
Dose level 3	3 mg orally on days 1-28	3 mg orally on days 1-21
Dose level 4	4 mg orally on days 1-28	4 mg orally on days 1-21

Dose escalation will continue in 1 mg increments until the MTD is reached. Once the MTD has been determined, an additional 6 patients will be treated at this dose level.

Patients will continue receiving treatment until either disease progression or unacceptable toxicity develops.

STUDY ENDPOINTS

- **Primary:** 1) The primary endpoint is the maximum tolerated dose (MTD) of pomalidomide in patients with symptomatic Waldenström macroglobulinemia (WM) whose disease has relapsed/and or is refractory to at least 1 prior line of therapy. Tolerability of a given dose will be assessed after every 3 patients have been enrolled, until the maximum tolerated dose has been defined or, in the absence of dose limiting toxicities, the highest planned dose level is determined to have an acceptable toxicity profile.
- **Secondary:** 1)The safety and toxicity profile of pomalidomide will be evaluated after all patients to be enrolled have completed 1 cycle of therapy; patients who received at least 1 dose of pomalidomide will be eligible for evaluation.
2) The efficacy of pomalidomide will be measured as best response to therapy. For each patient, this will be determined at the completion of their course of therapy. The collective data will be summed at study completion. Patients will be considered evaluable if they have completed at least 1 cycle of therapy.

STUDY DURATION: 3 years (expected)	TOTAL SAMPLE SIZE: maximum of 30
DOSING REGIMEN(S): Schedule A: Dose level 1 : 1 mg orally on days 1-28 Dose level 2 : 2 mg orally on days 1-28 Dose level 3 : 3 mg orally on days 1-28 Dose level 4 : 4 mg orally on days 1-28 Schedule B: Dose level 1: 1 mg orally on days 1-21 Dose level 2: 2 mg orally on days 1-21 Dose level 3: 3 mg orally on days 1-21 Dose level 4: 4 mg orally on days 1-21	STUDY DRUG SUPPLIES: Celgene Corporation will supply pomalidomide as 0.5 mg, 1.0 mg and 2.0 mg

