6.1 Overall design

[figure not shown]
This is a Phase 1 study of single agent pomalidomide in patients with symptomatic Waldenström macroglobulinemia (WM) whose disease has relapsed/and or is refractory to at least 1 prior line of therapy.

To determine the maximum tolerated dose (MTD), patients will be enrolled in cohorts of 3, and the study will follow a standard 3+3 statistical dose-finding design as outlined in Section 11.0. Once the maximum tolerated dose has been determined, and additional 6 patients will be enrolled at that dose level to better assess the safety and toxicity profile of that dose and schedule.

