6.4 Drug Administration

6.4.1 Treatment assignments

This is a Phase I non-randomized study. Eligible patients will be allocated to treatment in the order in which they sign the informed consent and that all documentation needed to confirm eligibility has been completed. A maximum of 30 subjects will be enrolled and treated with single agent pomalidomide. Starting at dose level 1 in Schedule A, the study will enroll patients in cohorts of 3, following a standard 3 +3 statistical design. (see Section 11.0).

Definition of Dose Limiting Toxicity (DLT):

Toxicity will be evaluated according to the NCI CTCAE version 4.0, (see Appendix E)

1) Non-hematologic dose limiting toxicity (DLT) is defined as any grade ≥ 3 non-hematological toxicity occurring during the first 28 days (first cycle) of treatment, with the specific exception of:

- Isolated Grade 3 elevation of liver function tests (LFTs) without associated clinical symptoms, lasting for ≤ 7 days in duration.
- Isolated Grade 3 elevation of amylase without associated clinical symptoms
- Grade 3 hypocalcemia, hypokalemia, hypomagnesemia, hyponatremia, or hypophosphatemia which responds to medical intervention.

2) Hematological dose limiting toxicity is defined as Grade ≥ 3 neutropenia with fever ≥ 38.5 , Grade 4 neutropenia lasting for ≥ 7 days in duration, or any Grade 4 anemia or thrombocytopenia occurring during the first 28 days (first cycle) of treatment.

Definition of Maximum Tolerated Dose (MTD): MTD is defined as the highest dose level in which 6 patients have been treated with less than 2 instances of DLT.

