6.4.2 Dosing regimen

There are four predefined dose levels (1, 2, 3, and 4) for pomalidomide, and two alternative dosing schedules (A and B). With schedule A, patients will be treated with the study drug for 28 days within each cycle. With schedule B, patients will be treated for 21 days within each 28 day cycle. Schedule B will only be explored if the MTD is exceeded at dose level 1 within Schedule A. The first cohort of 3 patients will be treated at dose level 1 with schedule A (28-day dosing). If no dose limiting toxicities (DLTs) are observed then the next cohort of 3 patients will be treated at next higher dose level. If one DLT is observed then 3 more patients will be treated at the same dose level. At anytime if 2 or more DLTs are observed within 3 or 6 patients at dose level 1, then schedule A is considered too toxic and will be abandoned. Patient enrollment will then be resumed using dose level 1 of dosing schedule B (21-day dosing) to determine the MTD. The purpose of schedule B is to prepare for the scenario that dosing schedule A is not tolerable.

Table 1

	Dosing Schedule A	Dosing Schedule B
Dose level 1	1 mg orally on days 1-28	1 mg orally on days 1-21
Dose level 2	2 mg orally on days 1-28	2 mg orally on days 1-21
Dose level 3	3 mg orally on days 1-28	3 mg orally on days 1-21
Dose level 4	4 mg orally on days 1-28	4 mg orally on days 1-21

Dose escalation will continue in 1 mg increments until the MTD is reached. Once the MTD has been determined, an additional 6 patients will be treated at this dose level.

An additional 6 patients will be treated at the MTD.

Dosing will be each night at approximately the same time. Pomalidomide should be taken with a glass of water on an empty stomach. **Only enough pomalidomide for one cycle of therapy will be supplied to the patient each cycle.**

Patients will continue receiving treatment with pomalidomide until disease progression or unacceptable toxicity develops.

Patients are to receive oral aspirin (325mg) as prophylactic anti-thrombotic treatment unless it is contraindicated, or the patient has a platelet count of less than 50,000. If the patient is intolerant of aspirin and has a platelet count of 50,000 or greater, the investigator is to prescribe therapeutic dose warfarin or low molecular weight heparin.

Pomalidomide capsules should be swallowed whole, and should not be broken, chewed or opened. Pomalidomide should be taken without food, at least 2 hours before or 2 hours after a meal.

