The standard “3+3” design is applied with 4 pre-defined dose levels. The first cohort of 3 patients will be treated at dose level 1 with schedule A (28-day dosing). If no DLT is observed then the next cohort of 3 patients will be treated at next higher dose level. If one DLT is observed then 3 more patients will be treated at the same dose level. At anytime if 2 or more DLTs are observed within 3 or 6 patients at dose level 1, then schedule A is considered too toxic and will be abandoned. The trial will then be restarted at dose level 1 using dosing schedule B (21-day dosing) to determine the MTD. If dose level 1 with schedule A is well tolerated (less than 2 DLT), then the MTD will be determined with dosing schedule A, and dosing schedule B will not be used. The purpose of schedule B is to prepare for the scenario that dosing schedule A is not tolerable.

	Dosing Schedule A	Dosing Schedule B
Dose level 1	1 mg orally on days 1-28	1 mg orally on days 1-21
Dose level 2	2 mg orally on days 1-28	2 mg orally on days 1-21
Dose level 3	3 mg orally on days 1-28	3 mg orally on days 1-21
Dose level 4	4 mg orally on days 1-28	4 mg orally on days 1-21

The “3+3” algorithm is as follows: (1) If 0 out of 3 patients experiences DLT at the end of first cycle, the next cohort of 3 patients will be treated at the next higher dose level. (2) If 1 out of 3 patients develop a DLT, an additional 3 patients will be treated at the same dose level. If no more DLTs develop at this dose, i.e. 1 out of a total of 6 patients develops a DLT, the dose escalation will continue for the next cohort of 3 patients. (3) At any given dose, if more than 1 out 3 patients or 1 out of 6 patients experience DLT, the dose level exceeds the MTD and 3 more patients will be treated at the next lower dose if there are less than 6 patients already treated at that dose. Following the above scheme, MTD is defined as the highest dose level in which 6 patients have been treated with less than 2 instances of DLT.

Analysis Plan

Toxicity data will be summarized using frequency tables. The types and severity of toxicity will be evaluated.

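### Section 11.6 counts 30 patients for dose finding alone, but the synopsis and 6.4.1 make 30 the whole-trial maximum; with the 6-patient expansion, 11.6's own premise gives 36

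*Combined protocol and SAP*

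**What the plan says.** Section 11.6 (Sample size and power considerations) states that "it is anticipated that up to 30 eligible patients are required for the dose-finding portion of this phase I trial". Its stated basis is four predefined dose levels and a possible change to Schedule B once 6 patients have been treated at level 1 of Schedule A. It does not mention an expansion cohort.

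Two other places apply the same number to the whole trial. The synopsis has "TOTAL SAMPLE SIZE: maximum of 30", and section 6.4.1 has "A maximum of 30 subjects will be enrolled and treated with single agent pomalidomide".

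Three places add an expansion. The synopsis says "Once the MTD has been determined, an additional 6 patients will be treated at this dose level" and section 6.4.2 says "An additional 6 patients will be treated at the MTD". Section 6.1 gives the purpose: "additional 6 patients will be enrolled at that dose level to better assess the safety and toxicity profile of that dose and schedule".

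Section 11.4.1 ties the end of recruitment to the cap: "Accrual will continue until maximum number of patients reaches or the trial is terminated according to the monitoring rules".

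On the switch of schedule, section 11.1 (like the synopsis and 6.4.2) begins its rule with "At anytime if 2 or more DLTs are observed within 3 or 6 patients at dose level 1", after which Schedule A is dropped. Section 11.1 also says that Schedule B is not used if level 1 of Schedule A is tolerated. Section 6.2 expects about 21 subjects to be screened.

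**The concern.** One number carries two meanings. If 30 is what dose finding may need, it cannot also be the ceiling for dose finding plus a further 6 patients. The 6 are not already inside the dose-finding count: the MTD definition in 6.4.1 and 11.1 itself requires 6 treated patients, and the expansion starts only after the MTD has been determined.

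The expansion is what is at stake. Accrual ends at the maximum, so on a long Schedule B path a cap of 30 would shorten or remove the cohort that 6.1 intends for a better safety assessment at the chosen dose. The team would then have to exceed the enrolment limit or omit planned safety data, and the documents do not say whether a shortened expansion is acceptable.

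**Working it through.** **Inputs from the documents**

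- 4 dose levels per schedule (11.1, 11.6).
- Cohorts of 3, enlarged to 6 after one DLT; at most 6 per level in dose finding (11.1).
- The MTD requires 6 treated patients with fewer than 2 DLTs (6.4.1, 11.1).
- A move to Schedule B after up to 6 patients at level 1 of Schedule A, restarting at level 1 (11.6, 11.1).
- Expansion of 6 after the MTD is determined (synopsis, 6.1, 6.4.2).

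**The plan's own figure.** Section 11.6 prints no sum, but its ingredients give

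6 (Schedule A, level 1) + 4 × 6 (Schedule B) = 30.

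This matches exactly, so 30 is the dose-finding maximum on that premise.

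**Adding the expansion**

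| Path | Dose-finding maximum | Expansion | Total |
|---|---|---|---|
| Schedule A only | 4 × 6 = 24 | 6 | 30 |
| Schedule A dropped after 3 patients, then B | 3 + 24 = 27 | 6 | 33 |
| Schedule A dropped after 6 patients, then B (11.6) | 6 + 24 = 30 | 6 | 36 |
| Literal reading of the switch rule | 24 + 24 = 48 | 6 | 54 |

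Against a cap of 30, the 11.6 path exceeds it by 6, and 6/30 = 20%. Places left for expansion under the cap are 30 − 27 = 3 if dose finding uses 27, and 30 − 30 = 0 if it uses 30. A total of 30 is guaranteed to suffice only if the trial stays on Schedule A; shorter Schedule B paths may also fit.

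The last row arises because the switch rule, read literally, also covers level 1 of Schedule A failing after escalation and step-down. Section 11.6 does not contemplate that case.

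**How often the cap would bind.** The documents give no DLT rates, so the rates below are assumptions. Every path of the 11.1 algorithm was enumerated exactly, with 6 patients required at the MTD and 6 added if an MTD exists. On 11.6's premise, Schedule B opens only if level 1 of Schedule A fails before any escalation.

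| Assumed DLT rates, levels 1–4, Schedule A / Schedule B | P(B used), 11.6 premise | P(total > 30), 11.6 premise | Expected total, 11.6 premise | P(total > 30), literal reading |
|---|---|---|---|---|
| .05 .10 .15 .20 / .04 .08 .12 .16 | 2.7% | 0.2% | 22.3 | 0.2% |
| .10 .20 .30 .40 / .075 .15 .225 .30 | 9.4% | 0.8% | 21.2 | 1.2% |
| .20 .30 .40 .50 / .15 .225 .30 .375 | 29% | 1.7% | 20.0 | 2.9% |
| .30 .40 .50 .60 / .15 .20 .25 .30 | 51% | 3.2% | 20.1 | 5.6% |
| .40 .50 .60 .70 / .10 .15 .20 .25 | 69% | 4.4% | 21.9 | 8.0% |
| .50 .60 .70 .80 / .10 .15 .20 .25 | 83% | 4.5% | 22.6 | 7.4% |

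On 11.6's premise the chance that dose finding alone uses all 30 is at most 0.5%. Given that Schedule B opens, the chance of exceeding 30 is about 5% to 8% (for example 4.4/69 ≈ 6%). Four further profiles, with level 1 of Schedule A at .35 to .50 and other Schedule B rates, gave 2.7% to 4.2% for P(total > 30) and 18.8 to 23.9 for the expected total.

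**The screening figure.** About 21 screened (6.2) is close to expected enrolment but below the 30 who may be enrolled. It is an approximate figure, and the discrepancy is minor.

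**The case against.** The best defence is that 30 means 24 + 6: Schedule A in full plus the expansion. The sum works, but it is not the basis 11.6 gives, which includes Schedule B and names dose finding only. If it was the intention, 11.6 is misworded and the total makes no allowance for Schedule B.

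A second defence is that the arithmetic in 11.6 is right and only the scope label differs, so this is an inconsistency rather than a miscalculation. That is a fair description, but the stated maximum still conflicts with the plan's own design.

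Third, the practical effect is small. The cap rarely binds, dose finding on 11.6's premise cannot exceed 30, and so the primary endpoint is never blocked; only a descriptive expansion can be trimmed. This stands and limits the weight of the point. It can also be said that 11.4.1 and 6.4.1 together do settle what happens at 30: accrual stops. That is so, but it leaves the instruction to treat 6 more at the MTD unmet, with no statement of whether a partial expansion is acceptable.

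Finally, 36 is not a safe ceiling for treated patients. Section 11.2 leaves out of the MTD determination those who withdraw before completing a cycle for reasons other than toxicity, and no replacement allowance is stated. This also stands, and any restated maximum should address it.

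**Conclusion.** The concern holds. Section 11.6 attaches 30 to dose finding on a basis that reproduces exactly, while the synopsis and 6.4.1 attach it to the whole trial. With the planned expansion, 11.6's premise gives 36, a gap of 6 patients or 20%. The shortfall is a worst case: under the six assumed rate profiles the probability of needing more than 30 is 0.2% to 4.5% on 11.6's premise, and 0.2% to 8.0% if the switch rule is read literally. Those percentages depend on DLT rates that are not in the documents; the 30-versus-36 conflict does not.

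The figure of 36 assumes that the switch comes after at most 6 patients at level 1 of Schedule A with no earlier escalation, and that every counted patient is evaluable. The point should be fixed, but it does not disturb the DLT rules, the MTD definition or the analysis sets.

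**What to change.** Amend the synopsis, 6.4.1 and 11.6 together, in one of two ways:

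- **(a)** State three numbers separately: dose-finding maximum 30, expansion 6, total 36.
- **(b)** Keep 30 as the total, reword 11.6 so that 30 no longer describes dose finding alone, and state how the cap limits the expansion if Schedule B is used.

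In either case:

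- Section 11.6 already names the 6 patients at level 1 of Schedule A; add that the count assumes no prior escalation.
- Reconcile that premise with the switch wording in the synopsis, 6.4.2 and 11.1, since the maximum is not final until this is settled.
- Say whether the maximum counts evaluable or treated patients, and whether non-evaluable patients are replaced.
- Bring the approximate screening number in 6.2 into line with the number who may be enrolled.

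The cost is a text correction. Option (a) raises the stated maximum by 6 and leaves expected enrolment unchanged. Option (b) leaves the maximum alone and lowers enrolment only on the rare paths where the cap binds.

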12.1 Institutional Review Board/Ethics Committee approval

The protocol for this study has been designed in accordance with the general ethical principles outlined in the Declaration of Helsinki. The review of this protocol by the IRB/EC and the performance of all aspects of the study, including the methods used for obtaining informed consent, must also be in accordance with principles enunciated in the declaration, as well as ICH Guidelines, Title 21 of the Code of Federal Regulations (CFR), Part 50 Protection of Human Subjects and Part 56 Institutional Review Boards.

The Investigator will be responsible for preparing documents for submission to the relevant IRB/EC and obtaining written approval for this study. The approval will be obtained prior to the initiation of the study.

The approval for both the protocol and informed consent must specify the date of approval, protocol number and version, or amendment number.

Any amendments to the protocol after receipt of IRB/EC approval must be submitted by the Investigator to the IRB/EC for approval. The Investigator is also responsible for notifying the IRB/EC of any serious deviations from the protocol, or anything else that may involve added risk to subjects.

Any advertisements used to recruit subjects for the study must be reviewed and approved by the IRB/EC prior to use.

12.2 Informed consent

The Investigator must obtain informed consent of a subject or his/her designee prior to any study related procedures as per GCPs as set forth in the CFR and ICH guidelines.

Documentation that informed consent occurred prior to the subject's entry into the study and the informed consent process should be recorded in the subject's source documents. The original consent form signed and dated by the subject and by the person consenting the subject prior to the subject's entry into the study, must be maintained in the Investigator's study files.

12.3 Subject confidentiality

Celgene affirms the subject's right to protection against invasion of privacy. In compliance with United States federal regulations, Celgene requires the Investigator to permit Celgene's representatives and, when necessary, representatives of the FDA or other regulatory authorities to review and/or copy any medical records relevant to the study in accordance with local laws.

Should direct access to medical records require a waiver or authorization separate from the subject's statement of informed consent, it is the responsibility of the Investigator to obtain such permission in writing from the appropriate individual.

12.4 Study records requirements

The Investigator must ensure that the records and documents pertaining to the conduct of the study and the distribution of the study drug, that is copies of CRFs and source documents (original documents, data, and records [e.g., hospital records; clinical and office charts; laboratory notes; memoranda; subject's diaries or evaluation checklists; SAE reports, pharmacy dispensing records; recorded data from automated instruments; copies or transcriptions certified after verification as being accurate copies; microfiches; photographic negatives, microfilm, or magnetic media; x-rays; subject files; and records kept at the pharmacy, at the laboratories, and at medico-technical departments involved in the clinical study; documents regarding subject treatment and study drug accountability; original signed informed consents, etc.]) be retained by the Investigator for as long as needed to comply with national and international regulations (generally 2 years after discontinuing clinical development or after the last marketing approval). The Investigator agrees to adhere to the document/records retention procedures by signing the protocol.

12.5 Premature discontinuation of study

12.5.1 Single center

The responsible local clinical Investigator as well as Celgene has the right to discontinue this study at any time for reasonable medical or administrative reasons in any single center. Possible reasons for termination of the study could be but are not limited to:

- Unsatisfactory enrollment with respect to quantity or quality.
- Inaccurate or incomplete data collection.
- Falsification of records.
- Failure to adhere to the study protocol.


Appendices

Appendix A: Pomalidomide Risks of Fetal Exposure, Pregnancy Testing Guidelines and Acceptable Birth Control Methods

Risks Associated with Pregnancy

Pomalidomide was found to be teratogenic in a developmental study in rabbits.

Pomalidomide is an analogue of thalidomide. Thalidomide is a known human teratogen that causes severe life-threatening human birth defects. If Pomalidomide is taken during pregnancy, it may cause birth defects or death to an unborn baby.

Criteria for females of childbearing potential (FCBP)

This protocol defines a female of childbearing potential as a sexually mature woman who: 1) has not undergone a hysterectomy or bilateral oophorectomy or 2) has not been naturally postmenopausal (amenorrhea following cancer therapy does not rule out childbearing potential) for at least 24 consecutive months (i.e., has had menses at any time in the preceding 24 consecutive months).

Counselling

For a female of childbearing potential, pomalidomide is contraindicated unless all of the following are met (i.e., all females of childbearing potential must be counselled concerning the following risks and requirements prior to the start of pomalidomide study therapy):

- She understands the potential teratogenic risk to the unborn child
- She understands the need for effective contraception, without interruption, 28 days before starting study treatment, throughout the entire duration of study treatment, dose interruption and 28 days after the end of study treatment
- She should be capable of complying with effective contraceptive measures
- She is informed and understands the potential consequences of pregnancy and the need to notify her study doctor immediately if there is a risk of pregnancy
- She understands the need to commence the study treatment as soon as pomalidomide is dispensed following a negative pregnancy test
- She understands the need and accepts to undergo pregnancy testing based on the frequency outlined in this protocol (Section 2).
- She acknowledges that she understands the hazards and necessary precautions associated with the use of pomalidomide

The investigator must ensure that females of childbearing potential:

- Comply with the conditions for pregnancy risk minimization, including confirmation that she has an adequate level of understanding
- Acknowledge the aforementioned requirements

For a female NOT of childbearing potential, pomalidomide is contraindicated unless all of the following are met (i.e., all females NOT of childbearing potential must be counselled concerning the following risks and requirements prior to the start of pomalidomide study therapy):

- She acknowledges that she understands the hazards and necessary precautions associated with the use of pomalidomide

The effect of pomalidomide on spermatogenesis is not known and has not been studied. Therefore, male patients taking pomalidomide must meet the following conditions (i.e., all males must be counselled concerning the following risks and requirements prior to the start of pomalidomide study therapy):

- Understand the potential teratogenic risk if engaged in sexual activity with a woman of childbearing potential
- Understand the need for the use of a condom even if he has had a vasectomy, if engaged in sexual activity with a female of childbearing potential.

Contraception

Females of childbearing potential (FCBP) enrolled in this protocol must agree to use two reliable forms of contraception simultaneously or to practice complete abstinence from heterosexual intercourse during the following time periods related to this study: 1) for at least 28 days before starting study drug; 2) while participating in the study; 3) dose interruptions; and 4) for at least 28 days after study treatment discontinuation.

The two methods of reliable contraception must include one highly effective method and one additional effective (barrier) method. FCBP must be referred to a qualified provider of contraceptive methods if needed. The following are examples of highly effective and additional effective methods of contraception:

- Highly effective methods:
 - Intrauterine device (IUD)
 - Hormonal (birth control pills, injections, implants)
 - Tubal ligation
 - Partner's vasectomy
- Additional effective methods:
 - Male condom
 - Diaphragm
 - Cervical Cap

Because of the increased risk of venous thromboembolism in patients with multiple myeloma taking pomalidomide and dexamethasone, combined oral contraceptive pills are not recommended. If a patient is currently using combined oral contraception the patient should switch to another one of the effective methods listed above. The risk of venous thromboembolism continues for 4–6 weeks after discontinuing combined oral contraception. The efficacy of contraceptive steroids may be reduced during co-treatment with dexamethasone.

Implants and levonorgestrel-releasing intrauterine systems are associated with an increased risk of infection at the time of insertion and irregular vaginal bleeding. Prophylactic antibiotics should be considered particularly in patients with neutropenia.

Pregnancy testing

Medically supervised pregnancy tests with a minimum sensitivity of 25 mIU/mL must be performed for females of childbearing potential, including females of childbearing potential who commit to complete abstinence, as outlined below.

Before starting study drug

Female Patients:

FCBP must have two negative pregnancy tests (sensitivity of at least 25 mIU/mL) prior to starting pomalidomide. The first pregnancy test must be performed within 10-14 days prior to the start of pomalidomide and the second pregnancy test must be performed within 24 hours prior to the start of pomalidomide. The patient may not receive study drug until the Investigator has verified that the results of these pregnancy tests are negative.

Male Patients:

Must practice complete abstinence or agree to use a condom during sexual contact with females of childbearing potential while participating in the study, during dose interruptions and for at least 90 days following study drug discontinuation, even if he has undergone a successful vasectomy.

During study participation and for 28 days following study drug discontinuation

Female Patients:

- FCBP with regular or no menstrual cycles must agree to have pregnancy tests weekly for the first 28 days of study participation and then every 28 days while on study, at study discontinuation, and at day 28 following study drug discontinuation. If menstrual cycles are irregular, the pregnancy testing must occur weekly for the first 28 days and then every 14 days while on study, at study discontinuation, and at days 14 and 28 following study drug discontinuation.
- At each visit, the Investigator must confirm with the FCBP that she is continuing to use two reliable methods of birth control at each visit.
- Counselling about pregnancy precautions and the potential risks of fetal exposure must be conducted at a minimum of every 28 days.

- If pregnancy or a positive pregnancy test does occur in a study patient, pomalidomide must be immediately discontinued.
- Pregnancy testing and counselling must be performed if a patient misses her period or if her pregnancy test or her menstrual bleeding is abnormal. Study drug treatment must be discontinued during this evaluation.
- Females must agree to abstain from breastfeeding during study participation and for at least 28 days after study drug discontinuation.

Male Patients:

- Counselling about the requirement for condom use during sexual contact with females of childbearing potential and the potential risks of fetal exposure must be conducted at a minimum of every 28 days.
- If pregnancy or a positive pregnancy test does occur in the partner of a male study patient during study participation, the investigator must be notified immediately.

Additional precautions

- Patients should be instructed never to give this medicinal product to another person and to return any unused capsules to the Investigator at the end of treatment.
- Patients should not donate blood during therapy and for at least 28 days following discontinuation of pomalidomide.
- Male patients should not donate semen or sperm during therapy or for at least 90 days following discontinuation of pomalidomide.
- Only enough pomalidomide for one cycle of therapy may be dispensed with each cycle of therapy.

